To evaluate the precision in terms of repeatability and reproducibility of an in-house developed software, called Calcify2D, that offers physicians a computer-assisted procedure to simultaneously score (and reduce scoring variability of) vascular calcifications (at the abdominal aorta and iliac arteries) and lumbar vertebral fractures (according to Quantitative Vertebral Morphometry principles) based on a latero-lateral thoracolumbar spine radiography. The software will be tested on clinical data from the VTP vs KYPHO study conducted recently at Istituto Ortopedico Rizzoli (IOR).

- Primary objective: to verify if the developed computer-assisted procedure reduces intra- and inter-observer variability in the computation of vascular calcifications at the abdominal aorta according to the Kauppila score
- Secondary objectives:
 - to verify if the developed computer-assisted procedure reduces intra- and inter-observer variability in the computation of lumbar vertebral fractures according to the principles of Quantitative Vertebral Morphometry
 - to produce preliminary data about the accuracy (i.e. accordance with measurements from accepted gold standard, taken as true) of the proposed computer-assisted scoring method for vascular calcifications, testing them against three-dimensional assessment from CT data (pending availability of matched CT data)
 - to produce preliminary data about the accuracy of the proposed computer-assisted scoring method for the existence of mild vertebral fractures, testing them against three-dimensional assessment of bone oedema from MRI data (pending availability of matched MRI data)

STUDY DESIGN

No-profit monocentric observational study to be conducted on the diagnostic images already collected at IOR within the VTP vs KYPHO study. From that study, diagnostic images of the thoracolumbar spine in different modalities (standard X-ray radiographies (Rx), CT, MRI) are available at several time points of follow-up and will be analysed in the present study.

Study workflow

- 1) Patient informed consent will be acquired
- 2) RX images showing VC will be used to assess whether the computer assisted VC scoring (primary objective) and Quantitative Vertebral Morphometry (QVM, limited to lumbar spine, secondary objective n.1) are less variable with respect to the traditional visual scoring of VC and QVM.

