- 3) The database will be searched for the existence of CT and MRI taken simultaneously (within one week) to the RX images. In case of positive findings, the study will proceed to the following steps.
- 4) Computer assisted Rx-based VC scoring will be compared to three dimensional CT quantitative VC computation (acting as gold standard) to produce preliminary data on its accuracy.
- 5) Computer assisted Rx-based QVM will be compared to three dimensional MRI data (acting as gold standard) to produce preliminary data on its accuracy in detecting mild vertebral fractures.

POPULATION

The present study relies on the data of the VTP vs KYPHO study. Data from the population of the VTP vs KYPHO study are particularly relevant and suitable for the scope of the present study since all subjects show vertebral fractures (sometimes multiple fractures), and there is a known association between vertebral fractures and VC. The VTP vs KYPHO study ran at IOR from 2009 to 2014 (Prot. gen. n. 30364 approved on 20.11.2009). Diagnostic images of the thoracolumbar spine in different modalities (RX, CT, MRI) were collected at several time points of follow-up for 109 patients.

All patients eligible for the study according to the following criteria will be contacted to acquire their informed consent to the participation in the study.

ELIGIBILITY CRITERIA

Inclusion criteria

- Patients included in the previous VTP vs KYPHO study.
- Presence of diagnostic images (Dorso-lumbar radiographies taken in latero-lateral projection).

- Rx images will be screened for the presence of VC, retaining only those showing VC.
- Informed consent obtained prior to any study analysis-evaluation and/or data collection.

Exclusion criteria

- Images of the patients included in the study VTP vs KYPHO showing severe artefacts (usually due to presence of metallic devices) that alter the grayscale range and hinder correct identification of VC and vertebral fractures will be excluded.

MATERIAL AND METHODS

Computation of VC score and QVM

Latero-lateral Rx images will be imported into the software Calcify2D. The software guides the clinician to subsequently:

- 1) identify the edges of vertebral endplates from T12 to L5 (lines connecting endplates define the regions of interest for the computation of abdominal aortic calcification score according to the current practice (Kauppila et al., 1997);

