- 2) measure the calcified plaques visible in the image, separating the anterior and posterior wall of the abdominal aorta, by tracing lines over them; a review of each traced line is possible; VC are then automatically scored according to the reference scoring system and to the absolute measure of calcification length;
- 3) refine vertebral contouring by picking a mid-side node on each vertebral endplate; QVM is then automatically computed;
- 4) review and save the report (with images) of VC and QVM issued automatically by the software application.

Observer variability tests on VC score and QVM

The test of observer variability will be performed by four clinicians from four relevant specialties, chosen among those who may often see VC and VF and are already familiar with the traditional scoring systems for both VC and VF (one radiologist and one spine orthopaedics from Istituto Ortopedico Rizzoli, one nefrologist and one internist from University of Padua).

Each clinician will assess all RX images to score VC and QVM, both via computer assisted procedures and via traditional visual inspection. To avoid bias, an interval of at least one week will be left between the computer assisted and visual scoring. To define intra-observer variability (i.e. repeatability), the whole dataset will be re-assessed three times, with an interval of at least one month between each re-assessment to avoid bias.

Preliminary assessment of the accuracy of computer assisted VC score and QVM against 3D data

In case time-matched CT data are available, the RX-based computer assisted VC score will be related to the current gold standard scoring system from CT (Takayama et al., 2016).

In case time-matched MRI data are available, they will be used to preliminary assess whether the RX-based computer assisted QVM can accurately detect mild vertebral fractures, which are detected with high sensitivity and specificity from MRI images because of the appearance of bone oedema.

STUDY END POINT**Primary Endpoint**

Observer variability (repeatability and reproducibility) in the assessment of vascular calcifications at the abdominal aorta according to a widely adopted scoring system (Kauppila et al., 1997): comparison between computer assisted and visual scoring.

Secondary Endpoints

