- a) Observer variability (repeatability and reproducibility) in the assessment of vertebral fractures in the lumbar spine according to Quantitative Vertebral Morphometry (Genant et al., 2000): comparison between computer assisted and visual scoring.
- b) Accuracy of computer assisted VC score (comparison with gold standard CT-based score)
- c) Accuracy of computer assisted QVM in detecting mild vertebral fractures (comparison with gold standard MRI detection)

STUDY PROCEDURES**Screening procedure and Enrollment procedures**

Patients considered eligible will be enrolled in the study, after providing a written informed consent.

Other study procedures

Study subjects will not be subjected to any clinical procedures, as the present study intends to perform a re-analysis of the imaging data already collected in a previous study, named VTP vs KYPHO.

DATA COLLECTION

Clinical data will be retrieved by patient's source document.

A protocol-specific CRF reporting the results of the VC scores and QVM will be provided.

DATA MANAGEMENT

Patient images will be pseudonymised. To avoid bias in the scoring, the four clinicians performing the study will be blind to any personal and clinical information.

CRFs will be handled centrally and filled with the data recorded for each patient (for each trial scoring for each clinician). Computer assisted scores will be automatically saved after each assessment. Visual scores will be annotated by each clinician in a session file.

DATA HANDLING PROCEDURES

Secure data transfer will be applied to send imaging data to the all the outcome assessors.

The PI will be responsible for the data pseudonymisation.

STATISTICS

Sample size considerations were made on the primary endpoint, i.e. observer variability of the VC score.

The most appropriate measure to assess observer variability has been identified in the Standard Error of the Measurement (SEM), less ambiguous than the often used Intra-class Correlation Coefficient according to a recent review (Popovic and Thomas, 2017).

It must be noted that there is currently no estimate of the Minimum Detectable Difference (MDD) of current methods for monitoring VC. Indeed, an estimate of the MDD for the current visual and the computer assisted scoring methods will be obtained from the SEM computed in the present study.

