Other statistical analyses for the primary endpoint will include further evaluation of intra- and inter-observer variability by the two-way ANOVA used to compute SEM (Eliasziw et al., 1994), Bland-Altman plots to assess agreement between methods, and Kappa statistics to assess inter-rater and inter-method agreement according to published thresholds (taking note of the above defined caveat about lack of consensus in threshold definition).

Additional analyses (per objective)

Objective 2 (observer variability in QVM): same analyses than in primary endpoint apply.

Objectives 3 and 4 (preliminary evaluation of the accuracy of computer-based assessment of VC and mild VF respectively against CT and MRI data): as we expect only few data points will be available, we plan to perform a simple correlation and residual analysis.

ETHICS AND QUALITY ASSURANCE

The clinical trial protocol and its documents will be sent before initiating the study to the competent Authorities and Ethics Committees for its approval.

The responsible investigator will ensure that this study is conducted in agreement with either the most updated Declaration of Helsinki and all the international and local laws that apply to clinical trials and to patient protection.

The protocol has been written, and the study will be conducted according to the principles of the ICH Harmonized Tripartite Guideline for Good Clinical Practice
(ref: <http://www.emea.eu.int/pdfs/human/ich/013595en.pdf>).

INFORMED CONSENT

All patients will be informed, by the investigator, of the aims of the study, the possible risks and benefits that will derive from the study participation.

The Investigator must clearly inform that the patient is free to refuse participation in the study and that can withdraw consent at any time and for any reason.

They will be informed as to the strict confidentiality of their patient data, but that their medical records may be reviewed for trial purposes by authorized individuals other than their treating physician.

The informed consent procedure must conform to the ICH guidelines on Good Clinical Practice. This implies that "the written informed consent form should be signed and personally dated by the patient or by the patient's legally acceptable representative".

The Investigator must also sign the Informed Consent form, and will keep the original at the site and a copy of the original must be handed to the patient.

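### Secondary endpoint c asks how well software QVM detects mild vertebral fractures against MRI, but the planned correlation and residual analysis does not commit to sensitivity or specificity

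*Combined protocol and SAP*

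**What the plan says.** Four places pose the question as one of existence or detection:

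- Objective of the Study, last secondary objective: "accuracy of the proposed computer-assisted scoring method for the existence of mild vertebral fractures", tested against a three-dimensional assessment of bone oedema on MRI, if matched MRI exists.
- Study workflow, step 5: the MRI comparison is made "to produce preliminary data on its accuracy in detecting mild vertebral fractures".
- Material and Methods, preliminary assessment of accuracy: whether software QVM "can accurately detect mild vertebral fractures, which are detected with high sensitivity and specificity from MRI images because of the appearance of bone oedema".
- Secondary Endpoints, item c: "Accuracy of computer assisted QVM in detecting mild vertebral fractures (comparison with gold standard MRI detection".

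The analysis is in Statistics, Additional analyses. Objectives 3 (calcification against CT) and 4 (mild fractures against MRI) share one sentence: "as we expect only few data points will be available, we plan to perform a simple correlation and residual analysis". Bland-Altman plots and Kappa are listed for the primary endpoint and carried over to Objective 2 only.

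In the Objective section, accuracy is defined generally, as "accordance with measurements from accepted gold standard, taken as true". No measure of it is named there.

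**The concern.** A detection question has two answers: how often the software misses a fracture that MRI shows, and how often it calls one that MRI does not show. The planned analysis commits to neither. Sensitivity and specificity appear once in the document, in Material and Methods, and there they describe MRI as the reference.

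The shared sentence suits Objective 3 better, because there both sides are scores. For Objective 4 the team could follow the plan to the letter and still not report how often the software misses or over-calls a mild fracture. What a reader could recover from the residuals would depend on a modelling choice that the plan leaves open.

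**Working it through.** **Plan's own figure.** There is none for endpoint c. The only precision figure, 6%, concerns the standard error of measurement of the calcification score and does not bear on this point. All accuracy values, prevalences, counts and the intraclass correlation (ICC) below are assumptions for illustration.

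**1. Correlation of two yes/no results.** Let Se be sensitivity, Sp specificity, p the proportion MRI-positive, and q = p·Se + (1 − p)(1 − Sp) the proportion software-positive. Then phi = (Se + Sp − 1) × √[p(1 − p) / (q(1 − q))].

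| Se | Sp | p | q | phi |
|---|---|---|---|---|
| 0.9 | 0.7 | 0.5 | 0.60 | 0.60 × √(0.25/0.24) = 0.61 |
| 0.7 | 0.9 | 0.5 | 0.40 | 0.60 × √(0.25/0.24) = 0.61 |
| 0.8 | 0.9 | 0.1 | 0.17 | 0.70 × √(0.09/0.1411) = 0.56 |
| 0.8 | 0.9 | 0.5 | 0.45 | 0.70 × √(0.25/0.2475) = 0.70 |

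Rows 1 and 2: a tool that over-calls and a tool that misses have the same coefficient. Rows 3 and 4: the coefficient moves although accuracy does not.

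**2. Residuals, software result regressed on MRI.** Intercept = 1 − Sp and slope = Se + Sp − 1. A miss has residual −Se and a false alarm has residual +Sp.

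- 0.9/0.7: intercept 0.30, slope 0.60, miss −0.9, false alarm +0.7.
- 0.7/0.9: intercept 0.10, slope 0.60, miss −0.7, false alarm +0.9.

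In this direction the residuals carry sensitivity and specificity.

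**3. Residuals, MRI regressed on the software result.** A false alarm has residual −PPV, where the positive predictive value is PPV = p·Se/q. With 0.8/0.9 fixed:

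- p = 0.1: −0.08/0.17 = −0.47.
- p = 0.5: −0.40/0.45 = −0.89.

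In this direction the residuals carry predictive values, which shift with prevalence. The plan does not say which direction it means.

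**4. What a 2x2 table would deliver with few data.** Assume 10 patients with 5 lumbar vertebrae each, one MRI-positive and four MRI-negative per patient. Exact (Clopper-Pearson) 95% intervals:

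- Sensitivity 8/10: 44-97%.
- Specificity 36/40, ignoring clustering: 76-97%.
- Specificity with ICC 0.2: design effect 1 + 3 × 0.2 = 1.6, effective n = 40/1.6 = 25, interval about 71-98%.

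**5. Which reading is compared.** The sample-size text has four observers analysing the images three times, so each image has 4 × 3 = 12 computer-assisted readings. The plan does not say which of them is set against MRI.

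**The case against.** The strongest reply is that the analysis is modest by design. It is secondary, labelled preliminary, runs only if matched MRI exists, and the plan says openly that few data points are expected. No sample size or decision rests on it. That stands, and it limits the importance of the point. It does not favour correlation, because a table of counts with exact intervals needs no minimum number and shows the uncertainty directly.

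Second, the yes/no format is not certain. Accuracy is defined generally, and a three-dimensional assessment of oedema could be graded. That also stands. However, no graded MRI measure is defined, and endpoint c is worded as detection.

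Third, residual analysis can recover sensitivity and specificity. It can, under the direction in step 2, but the plan does not commit to it.

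Three stronger readings are tempting, and the documents do not support them:

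- A reader might infer that X-ray and MRI are not matched in time. Study workflow step 3 requires them to be within one week of each other. Only the handling of several pairs from one patient is open.
- A reader might infer that the cut-off for a mild fracture will be chosen after the data are seen. The Background ties QVM to a named fracture classification, which the secondary endpoints cite again. The source is not available here, so whether it settles the cut-off cannot be checked, and a post-hoc choice is not established.
- A reader might infer from "all subjects show vertebral fractures (sometimes multiple fractures" that a per-patient table would have almost no negatives. That sentence does not say that the fractures are mild, lumbar or oedematous on the matched MRI.

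**Conclusion.** The mismatch holds. Endpoint c is a detection question, and the only analysis assigned to it does not commit to reporting misses and over-calls. The conclusion rests on reading the existence and detection wording as a yes/no comparison, which is the most natural reading but an inferred one. The numerical examples show the mechanism; they do not predict this study's results, since the documents give neither a prevalence nor a number of matched MRI examinations.

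The impact is minor and the point is a cheap improvement. The primary endpoint, its sample size and Objective 2 are unaffected. Nothing here counts against correlation and residuals for Objective 3.

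**What to change.** In Statistics, Additional analyses, give Objective 4 its own paragraph:

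- **Data:** the X-ray/MRI pairs matched within one week under Study workflow step 3.
- **Main summary:** a 2x2 table per lumbar vertebra of software-QVM mild fracture (yes/no) against MRI oedema (yes/no). Define the software result in advance from the categories of the classification that the protocol already cites, including how a vertebra graded above mild is counted.
- **Reporting:** raw counts, and sensitivity and specificity with exact 95% intervals. Where numbers allow, widen these for clustering of vertebrae, repeated pairs and repeated readings within a patient.
- **Reading:** state which of the 12 computer-assisted readings per image enters the table.
- **Supplement:** keep correlation and residuals, with the model and its direction stated.

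Record the vertebra-level MRI result alongside the QVM result. Data Collection says "A protocol-specific CRF reporting the results of the VC scores and QVM will be provided"; this does not rule out an MRI field but does not mention one.

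The cost is a short paragraph and a recording field, with no new patients, images or X-ray readings. The MRI assessment is already planned but would have to be recorded vertebra by vertebra. The intervals will be wide.
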